6.3. Multi-Center Studies

This is a multi-center study enrolling subjects from 33 US sites. The number of subjects per site might be small. Therefore, there are no analyses adjusting for sites.

6.4. Multiple Comparisons / Multiplicity

To control the overall Type I error rate across the seven hypothesis tests involving the primary endpoint and the key secondary endpoints (listed below) at the 0.05 level (two-sided), a fixed sequence procedure will be implemented. The hypothesis tests will be assessed sequentially as follows:

1. Non-inferiority of 0.002% DE-117 to 0.5% Timolol Maleate for the primary endpoint, IOP at each scheduled timepoint (08:00, 10:00, and 16:00) at Week 1, Week 6, and Month 3.
2. Non-inferiority of 0.002% DE-117 to 0.5% Timolol Maleate for the first key secondary endpoint, mean diurnal IOP at Month 3.
3. Non-inferiority of 0.002% DE-117 to 0.5% Timolol Maleate for the second key secondary endpoint, IOP at each scheduled timepoint (08:00, 10:00, and 16:00) at Week 1, Week 6, and Month 3 in the study eyes with mean diurnal IOP < 25 mmHg at the Baseline Visit.

4. Superiority of 0.002% DE-117 to 0.5% Timolol Maleate for the third key secondary endpoint, mean diurnal IOP at Week 1.
5. Superiority of 0.002% DE-117 to 0.5% Timolol Maleate for the first key secondary endpoint, mean diurnal IOP at Month 3.
6. Superiority of 0.002% DE-117 to 0.5% Timolol Maleate for the second key secondary endpoint, IOP at each scheduled timepoint (08:00, 10:00, and 16:00) at Week 1, Week 6, and Month 3 in the study eyes with mean diurnal IOP < 25 mmHg at the Baseline Visit.
7. Superiority of 0.002% DE-117 to 0.5% Timolol Maleate for the primary endpoint, IOP at each scheduled timepoint (08:00, 10:00, and 16:00) at Week 1, Week 6, and Month 3.

The second hypothesis testing 2) will be tested only if the first hypothesis 1) is rejected. The third hypothesis testing 3) will be tested only if the second hypothesis 2) is rejected, and so on.

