#### 14.3.2. Statistical Hypotheses and Level of Significance

The primary efficacy endpoint is the IOP in the study eye measured at the specified time points: 08:00, 10:00 and 16:00 at Week 1, Week 6 and Month 3 visits.

For the primary endpoint, a Mixed Effect Model for Repeated Measurement (MMRM) will be used to test the following hypotheses:

$$H_0: \mu_T - \mu_C > \Delta \text{ versus } H_A: \mu_T - \mu_C \leq \Delta$$

where  $\mu_T$  and  $\mu_C$  denote the mean values of the primary endpoint in DE-117/Vehicle arm and Timolol Maleate arm, respectively, and  $\Delta$  denotes the non-inferiority margin of 1.5 mmHg.

Treatment difference between the DE-117/Vehicle arm and Timolol Maleate arm at each specified time point of each post-baseline visit up to Month 3 will be reported along with 95% confidence intervals. Non-inferiority is established if the upper limit of the two-sided 95% confidence interval for the difference in the mean IOP (0.002% DE-117 - Timolol Maleate) is  $\leq 1.5$  mmHg at all nine time points and  $\leq 1.0$  mmHg in majority (5 or more) of the time points. If the upper limit of the 95% confidence interval for the difference is  $\leq 0$  at all nine time points, superiority of DE-117 to Timolol will be claimed.

If non-inferiority in the primary endpoint is achieved, then the following two key secondary endpoints will be tested sequentially according to hierarchical fixed sequence procedure:

1. Mean diurnal IOP in the study eye at Month 3

The corresponding hypothesis is:

$$H_{0S1}: \mu_{Ts1} - \mu_{Cs1} > \Delta \text{ versus } H_{AS1}: \mu_{Ts1} - \mu_{Cs1} \leq \Delta$$

where  $\mu_{Ts1}$  and  $\mu_{Cs1}$  denote the mean diurnal IOP at Month 3 in DE-117/Vehicle arm and Timolol Maleate arm, respectively; and  $\Delta$  denotes the non-inferiority margin of 1.5 mmHg.

If the hypothesis is rejected at 0.05 significance level, then the following key secondary endpoint will be tested:

2. Mean diurnal IOP in the study eye at Week 1

The corresponding hypothesis is:

$$H_{0S2}: \mu_{Ts2} = \mu_{Cs2} \text{ versus } H_{AS2}: \mu_{Ts2} \neq \mu_{Cs2}$$

Where  $\mu_{Ts2}$  and  $\mu_{Cs2}$  denote the mean diurnal IOP at Week 1 in DE-117/Vehicle arm and Timolol Maleate arm, respectively.

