#### **14.7.2. Analysis of Secondary Efficacy Endpoints**

##### **14.7.2.1. Key Secondary Efficacy Endpoints**

The key secondary efficacy endpoints are

- Mean diurnal IOP in the study eye at Month 3 (Visit 5), and
- Mean diurnal IOP in the study eye at Week 1 (Visit 3)

A MMRM will be carried out on observed cases up to Month 3. The least square mean diurnal IOP of each treatment arm and 95% confidence interval for the difference in least square means between DE-117/Vehicle and Timolol Maleate at Week 1 and Month 3 will be estimated, respectively. If non-inferiority in the primary endpoint is achieved, then the two key secondary endpoints will be tested sequentially at the 0.05 significance level (2-sided) to control the overall Type I error rate associated with the two comparisons.

The primary analysis will be based on the FAS. The same analysis will be repeated on the PPS population as a sensitivity analysis. More details on the model specifications and multiplicity adjustment will be provided in the SAP.

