Non-inferiority criteria for primary endpoint: With respect to the primary study objective, non-inferiority of DE-117 to Timolol is achieved if the upper limit of the two-sided 95% confidence interval for the difference in the mean IOP (DE-117 minus Timolol) is ≤ 1.5 mmHg at all nine timepoints and ≤ 1.0 mmHg at a majority (five or more) of the nine timepoints.

Superiority of DE-117 to Timolol for the primary efficacy endpoint is achieved if the upper limit of the two-sided 95% confidence interval for the difference in the mean IOP (DE-117 minus Timolol) is < 0 mmHg at all nine timepoints.

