8.1.1.2. Key Secondary Endpoints

8.1.1.2.1. Mean Diurnal IOP at Month 3

The first key secondary endpoint is mean diurnal IOP in the study eye at Month 3. The following null (versus alternative) hypothesis will be tested:

$$H_{0SI}: \mu_{TI} - \mu_{CI} \geq \Delta \text{ versus } H_{ASI}: \mu_{TI} - \mu_{CI} \leq \Delta$$

where μ_{TI} and μ_{CI} denote the mean diurnal IOP at Month 3 in the DE-117 and Timolol arm, respectively, and Δ denotes the non-inferiority margin of 1.5 mmHg. The primary analysis of this key secondary efficacy endpoint will be performed using a MMRM based on the FAS. The model will include treatment, analysis visit (Week 1, Week 6, or Month 3), and treatment-by-visit interaction as fixed effects, and baseline mean diurnal IOP as a covariate. Correlations of mean diurnal IOPs within-subject will be modeled using an unstructured covariance matrix. The mathematical model is analogous to the model in the primary efficacy endpoint.

If there are convergence issues, covariance matrix structures other than unstructured will be tried in the following order: (1) heterogeneous Toeplitz (TOEPH), (2) heterogeneous autoregressive of order 1 (ARH(1)), (3) heterogeneous compound symmetry (CSH), and (4) compound symmetry (CS). The first covariance structure that converges will be used as the primary analysis. Least squares mean diurnal IOP values at Month 3 for each treatment arm and the difference between least squares treatment group means and its 95% confidence interval will be reported.

Non-inferiority of DE-117 to Timolol is achieved for this endpoint if the upper limit of the 95% confidence interval for the difference between DE-117 and Timolol (DE-117 minus Timolol) in the mean diurnal IOP at Month 3 is ≤ 1.5 mmHg. Superiority of DE-117 to Timolol is achieved for this endpoint if the upper limit of the 95% confidence interval is < 0 mmHg.

8.1.1.2.2. IOP at Nine Timepoints in Study Eyes with Baseline Mean Diurnal IOP < 25 mmHg

The second key secondary endpoint is IOP at each scheduled timepoint (08:00, 10:00, and 16:00) at each of three follow-up visits, Week 1, Week 6, and Month 3, in the study eyes with mean diurnal IOP < 25 mmHg at the Baseline Visit. If non-inferiority of DE-117 to Timolol for the primary endpoint and the first key secondary endpoint is achieved, the following null (versus alternative) hypothesis will be tested for the second key secondary endpoint:

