$$H_{0S2}: \mu_{T2} - \mu_{C2} > \Delta, \text{ for at least one timepoint}$$

versus

$$H_{AS2}: \mu_{T2} - \mu_{C2} \leq \Delta \text{ at all nine timepoints}$$

where μ_{T2} and μ_{C2} denote the mean IOP values in the DE-117 arm and the Timolol arm, respectively, and Δ denotes the non-inferiority margin of 1.5 mmHg or 1.0 mmHg as specified below.

The same MMRM used in the analysis of the primary efficacy endpoint will be used for the analysis of the second key secondary endpoint. Non-inferiority of DE-117 to Timolol for this endpoint (i.e., for subjects with baseline mean diurnal IOP < 25 mmHg) is achieved if the upper limit of the two-sided 95% confidence interval for the difference in the mean IOP (DE-117 minus Timolol) is ≤ 1.5 mmHg at all nine timepoints and ≤ 1.0 mmHg at a majority (five or more) of the nine timepoints. Superiority of DE-117 to Timolol for this endpoint (i.e., for subjects with baseline mean diurnal IOP < 25 mmHg) is achieved if the upper limit of the two-sided 95% confidence interval for the difference in the mean IOP (DE-117 minus Timolol) is < 0 mmHg at all nine timepoints.

8.1.1.2.3. Mean Diurnal IOP at Week 1

The third key secondary endpoint is mean diurnal IOP in the study eye at Week 1. If non-inferiority of DE-117 to Timolol for the primary and the first two key secondary endpoints is achieved, then the following null (versus alternative) hypothesis will be tested for the third key secondary endpoint:

$$H_{0S3}: \mu_{T3} = \mu_{C3} \text{ versus } H_{AS3}: \mu_{T3} \neq \mu_{C3}$$

where μ_{T3} and μ_{C3} denote the mean diurnal IOP at Week 1 in the DE-117 and Timolol arm, respectively. The primary analysis of this key secondary endpoint will be performed using a MMRM analogous to the model used for the first key secondary efficacy endpoint (mean diurnal IOP at Month 3).

For the primary and key secondary efficacy endpoints, the testing sequence and multiplicity adjustment details are provided in [Section 6.4](#).

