10. ADDITIONS AND CHANGES TO THE PROTOCOL-SPECIFIED ANALYSES

10.1. Full Analysis Set Definition

The full analysis set definition has been updated to add the requirement that baseline IOP data has to be present:

The Full Analysis Set (FAS) will include all randomized subjects who received at least one dose of study medication and provided Baseline IOP data (at any timepoint) and at least one post-baseline IOP measurement (at any timepoint). Efficacy analyses will be performed using the FAS and summarized by treatment as randomized.

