10.2. Key Secondary Endpoint

An additional key secondary endpoint (IOP at each scheduled timepoint [08:00, 10:00, and 16:00] at Week 1 [Visit 3], Week 6 [Visit 4], and Month 3 [Visit 5] in the study eyes with mean diurnal IOP < 25 mmHg at the Baseline Visit) was added based on analysis results of a recently completed study in Asia.

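### Should SAP Section 10 record and justify that the SAP 6.4 testing order puts Week 1 superiority and full-population superiority behind the <25 mmHg subgroup tests?

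*SAP*

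**What the plan says.** **Protocol.** Section 14.3.2 starts with primary non-inferiority at nine timepoints. Two key secondary tests follow in fixed sequence: Month 3 mean diurnal non-inferiority, then Week 1 mean diurnal superiority. Outside that sequence it adds that, if the upper limit is at or below 0 "at all nine time points, superiority of DE-117 to Timolol will be claimed". There is no subgroup test. Section 14.7.2.1 repeats the two-step sequence and leaves further detail on models and multiplicity to the SAP.

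**SAP 6.4.** Seven tests run in fixed sequence: (1) primary non-inferiority; (2) Month 3 mean diurnal non-inferiority; (3) nine-timepoint non-inferiority in study eyes with baseline mean diurnal IOP below 25 mmHg; (4) Week 1 mean diurnal superiority; (5) Month 3 mean diurnal superiority; (6) nine-timepoint superiority in the subgroup; (7) nine-timepoint superiority in the full population. The gating rule is "The third hypothesis testing 3) will be tested only if the second hypothesis 2) is rejected, and so on".

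**SAP 8.1.1.** The Week 1 gate is restated in 8.1.1.2.3: "If non-inferiority of DE-117 to Timolol for the primary and the first two key secondary endpoints is achieved". The criterion for test 5 is in 8.1.1.2.1: "Superiority of DE-117 to Timolol is achieved for this endpoint if the upper limit of the 95% confidence interval is" below 0 mmHg. The criterion for test 7 is in 8.1.1.1: "Superiority of DE-117 to Timolol for the primary efficacy endpoint is achieved if the upper limit of the two-sided 95% confidence interval" lies below 0 at all nine timepoints.

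**SAP 10.** Under the heading "ADDITIONS AND CHANGES TO THE PROTOCOL-SPECIFIED ANALYSES" there are three entries: the FAS definition, the extra key secondary endpoint, and the removal of LOCF. Of the endpoint, 10.2 says that it "was added based on analysis results of a recently completed study in Asia". It does not mention the endpoint's place in the sequence, the two gates or test 5.

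**The concern.** A reader who uses Section 10 to see how the SAP departs from the protocol would miss three departures: the new gate on Week 1 superiority, the move of full-population superiority to last place behind a subgroup, and the added Month 3 superiority claim.

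The two documents can also disagree on the same data. Suppose all nine full-set upper limits are below 0 and one subgroup limit is above 0. Protocol 14.3.2 then supports superiority and SAP 6.4 does not. A subgroup is smaller than the whole, so making a full-population claim wait for it costs power. SAP 3.3 states power for the full sample only, and no reason for the order is given.

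**Working it through.** **1. Is any step left open?** No. Under SAP 6.4 each set of nine full-set limits, nine subgroup limits and two mean diurnal limits leads to one set of claims. SAP 1 makes the SAP analyses the basis of the study report, and protocol 14.3 has the SAP finalised before unmasking. Two analysts would reach the same result.

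**2. Is Type I error controlled?** Yes. Each test is run at two-sided 0.05 and only after every earlier rejection. A false claim therefore requires rejecting the first true null in the list, which has probability at most 0.05 whatever the order or the subgroup size.

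**3. The plan's own power figure.** Inputs from SAP 3.3: SD 4.0, correlation 0.6, 200 per arm, margin 1.5, difference 0, power 90%.
- SE = 4.0 × √(2/200) = 0.40. One timepoint: Φ(1.5/0.40 − 1.96) = Φ(1.79) = 96.3%.
- Full rule (≤1.5 at all nine, ≤1.0 at five or more), simulated with nine equally correlated differences: 72%.
- The SAP model adjusts for baseline. Assuming the baseline correlation is also 0.6, SD = 4.0 × √(1 − 0.6²) = 3.2, and the full rule gives 92%.

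The stated 90% lies between these and its formula is not given, so this does not show it to be wrong. It does mean that power figures at SD 4.0 alone would overstate the cost of some gates. Both SDs are shown below.

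**4. Cost of the gates.** The subgroup share f is not in the documents; 50% is assumed, with 30% to 70% in brackets. Effects are assumed equal inside and outside the subgroup. Method: 200,000 draws; full-set difference = f × subgroup + (1 − f) × rest; mean diurnal SD = SD × √((1 + 2 × 0.6)/3); limits at ±1.96 SE.

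| Quantity | SD 4.0 | SD 3.2 |
|---|---|---|
| Tests 1–3 all passed, difference 0 | 31% (14–49) | 57% (29–76) |
| Week 1 superiority, without → with gate 3: −1.0 throughout | 83 → 82% (64–83) | 95 → 95% (90–95) |
| −1.0 at Week 1, then −0.5 | 83 → 71% (43–81) | 95 → 93% (73–95) |
| −1.0 at Week 1, then 0 | 77 → 40% (19–58) | 94 → 68% (38–85) |
| Nine-timepoint superiority, protocol → SAP: difference 0 | about 0% both | about 0% both |
| −1.0 throughout | 32 → 8% (3–15) | 61 → 20% (8–35) |
| −1.5 throughout | 84 → 38% (16–60) | 98 → 68% (35–88) |

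The reason is the interval width. At SD 4.0 the half-width is 1.96 × 0.40 = 0.78 in the full set. With 100 per arm it is 1.96 × 4.0 × √(2/100) = 1.11. All the loss for test 7 comes from the subgroup steps: the same sequence without tests 3 and 6 keeps 84% at −1.5.

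**5. Would another order be better?**
- *Tests 3 and 4 exchanged.* At the planned difference of 0, a two-sided 5% test favours DE-117 with probability 2.5%. Subgroup non-inferiority would then be reached at most 2.5% of the time, so its chance of success would fall from 31% (57% at SD 3.2) to at most 2.5%.
- *Tests 6 and 7 exchanged* (SD 4.0, f = 50%, overall −1.0). With equal effects, test 7 rises from 8% to 32% and test 6 falls from 9% to 8%. If the subgroup does 1.5 mmHg better than the rest, test 7 rises from 29% to 32% and test 6 falls from 54% to 29%.

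Which order is preferable depends on the expected subgroup effect. SAP 10.2 says results from another study prompted the subgroup endpoint; those results are not in the documents.

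**The case for a change.** Section 10 sets its own standard. It records a small edit to the FAS definition and argues the removal of LOCF, and a change in when superiority may be claimed matters more than the FAS edit. Week 1 superiority is a stated secondary objective in both documents, while the <25 mmHg subgroup appears in no objective; yet failing test 3 blocks the Week 1 claim. The delegation in protocol 14.7.2.1 is also a weaker answer for Week 1, because the protocol had already fixed that order. Where an early benefit fades to nothing, the gate is costly at either SD.

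Most of this stands as description. Section 10 is incomplete, and the Week 1 gate departs from a stated protocol order. It does not show that anything in the analysis should change. The SAP nowhere says that Section 10 is exhaustive. The order is not hidden: 2.2.2 numbers the subgroup endpoint second of three, 6.4 lists all seven tests, and 8.1.1.2.3 spells out the Week 1 gate and points to 6.4. SAP 1 asks for justification of deviations from the SAP, not of every difference from the protocol. Neither document gives power for any key secondary test, so its absence for tests 3 and 6 is not peculiar to the subgroup. Nine-timepoint superiority is in no stated objective, and the protocol gave it no place in the sequence, so placing it is fairly the detail left to the SAP.

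**Conclusion.** The concern is right about the text and calls for no change. Section 10 omits both gates and test 5, but the rules are complete and unambiguous in SAP 6.4 and 8.1.1, and family-wise error is held at 0.05. Where protocol and SAP disagree on nine-timepoint superiority, the SAP is the stricter, so no unsupported claim can result. New Section 10 entries would restate what 6.4 already says. The difference between ≤0 (protocol 14.3.2) and <0 (SAP 8.1.1.1) has no practical effect on a continuous limit.

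The order is a fair trade-off. Its price is nil for nine-timepoint superiority at the planned difference of 0, and large only if DE-117 is truly better: at −1.5 mmHg and a 50% share, 84% falls to 38% at SD 4.0 and 98% to 68% at SD 3.2. For Week 1 superiority the cost runs from 1 point or less, when a 1 mmHg benefit persists, to 37 points (SD 4.0) or 26 points (SD 3.2), when it vanishes after Week 1. In return, subgroup non-inferiority keeps a realistic chance of being tested. These sizes rest on an assumed share, equal effects in and out of the subgroup, and an assumed baseline-adjusted SD. Tests 1 and 2, which carry the primary objective and the first secondary objective, are untouched.

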6.5. Interim Analysis

No interim analysis is planned for this study.

7. SUMMARY OF STUDY POPULATION DATA

7.1. Subject Disposition

The disposition of ITT population (i.e., all randomized subjects) will be summarized by treatment and overall. The summary will include the number and percentage of ITT subjects in the Safety population, FAS, and PPS. The disposition summary will also include the number and percentage of subjects who completed the study drug, subjects who discontinued the study drug prematurely but continued with study participation and among which who completed or not completed all study visits, as well as the number and percentage of subjects who discontinued from the study or discontinued from the study drug prior to Month 3 Visit by the primary discontinuation reason.

7.2. Demographics and Baseline Characteristics

Subject demographics and baseline characteristics will be descriptively summarized for the FAS by planned treatment. Specifically, for subject demographics, the following variables will be summarized:

- Age at randomization (continuous and categorical: < 65 years or \geq 65 years)
- Sex (categorical: Male or Female)
- Ethnicity (categorical: Hispanic/Latino or Not)
- Race (categorical: American Indian or Alaska Native, Asian, Black or African American, Native Hawaiian or Other Pacific Islander, White, or Other)

For baseline characteristics, the following variables will be summarized for study eye and fellow eye, separately:

- Primary ocular diagnosis (categorical: POAG, Pseudoexfoliative Glaucoma, Pigmentary Glaucoma, or OHT)
- Iris Color (categorical: Blue/Gray, Blue/Gray with Slightly Brown, Blue/Gray – Brown, Green, Green with Slightly Brown, Green – Brown, Yellow – Brown, or Brown)
- Prior use of IOP-lowering medications (categorical: oral/topical carbonic anhydrase inhibitors, alpha agonists, beta-blockers, prostaglandin/prostaglandin analogues, or none)
- Prostaglandin naive (Yes or No)
- Baseline lens status (categorical: phakic or pseudophakic/aphakic)
- Baseline mean diurnal IOP score and baseline IOP score at each scheduled timepoint (08:00, 10:00, and 16:00)
- BCVA (logMAR)
- Central corneal thickness (μ m)
- Glaucomatous optic nerve findings (categorical: none, mild, moderate, or severe)

- Anterior chamber angle classification (Shaffer scale; categorical: approximately 5 degrees or less, approximately 10 degrees, approximately 20 degrees, approximately 30 degrees, or approximately 40 degrees or more)
- Visual field (parameters: glaucoma Hemifield test, visual field mean deviation by device, and visual field pattern standard deviation by device)

7.3. Medical and Surgical History

For this study, medical and surgical history and adverse events will be coded using MedDRA 21.1, 2018. Each medical event will be classified into a SOC and mapped to a Preferred Term (PT).

The medical and surgical history will be summarized for the FAS. Subjects reporting any medical and surgical history at baseline will be tabulated by SOC and PT for each planned treatment and overall.

7.4. Protocol Deviations

In this study, protocol deviations are categorized as follows:

- Informed Consent
- Inclusion/Exclusion Criteria
- Concomitant Treatment
- Investigational Product
- Procedures/Tests/Assessments
- Laboratory
- Time Window
- Other

A protocol deviation is considered significant if it may affect the subject's rights, safety, or well-being, and/or the completeness, accuracy, or reliability of the study data. Santen's study team will review all protocol deviations and determine the list of significant protocol deviations prior to database lock. All randomized subjects with any significant protocol deviation(s) will be tabulated by deviation category for each planned treatment and overall. In addition, two listings will be provided: (1) all significant protocol deviations and (2) subjects excluded from the per protocol population.

7.5. Prior and Concomitant Medications

For this study, non-study medications, including prior and concomitant medications, will be coded using World Health Organization (WHO) Drug Global, Version September 2018, format B3. Each non-study medication will be classified using the Anatomical-Therapeutic-Chemical (ATC) classification system and mapped to a WHODrug preferred drug name.

Non-study medications will be summarized for the Safety population. Subjects taking any prior medications will be tabulated by ATC level 3, level 4, and preferred drug name for each actual

treatment received and overall. A subject will be counted at most once for each prior medication, even if the subject took the same prior medication on multiple occasions. Subjects taking any concomitant medications will be tabulated similarly. In addition, prior medications and concomitant medications will also be listed, separately.

